BL Baseline

CAI Condomless Anal Intercourse

CASI Commuter Assisted Self-Interview

CDC Centers for Disease Control and Prevention

CFAR Center for AIDS Research

CRF Case report form

DBS Dried blood spot

DSMB Data Safety Monitoring Board

DCF Data Collection Form

GLMM Generalized linear mixed models

HIPAA Health Insurance Portability and Accountability Act

HIV Human Immunodeficiency Virus

HMP HealthMpowerment

IGHID Institute for Global Health & Infectious Diseases

IRB Institutional Review Board

LGBTQ Lesbian, Gay, Bisexual, Transgender, and Queer

MSM Men who have sex with men

NIH National Institutes of Health

OCS One Cow Standing

PI Principal Investigator

PID Participant ID

OHRP Office of Human Research Protection

RCT Randomized controlled trial

SEM Structural equation modeling

SID Study ID number

SMS Short text message service

SSL Secure Socket Layer

UNC University of North Carolina

U. Penn University of Pennsylvania

VS Viral Suppression

YAB Youth Advisory Board

YBLMT Young Black or Latino men who have sex with men and transgender

women

YBMT Young Black men who have sex with men and transgender women

[figure not shown]
YMSM Young men who have sex with men

STUDY ABSTRACT

Multiple stigmas related to sexuality, race, and HIV infection negatively impact HIV testing, engagement in HIV care, and consistent viral suppression (VS) among young Black or Latino men who have sex with men and transgender women (YBLMT). At present, few interventions have addressed the effects of intersectional stigma among HIV-infected and uninfected populations. In response to the National Institutes of Health RFA-MH-18-606, this study tests whether a smartphone application (app) intervention tailored for intersectional stigma amelioration can elicit online social support, promote intervention engagement, and mitigate the impact of multiple stigmas on HIV-related outcomes. We will recruit and enroll 1,050 young (ages 15-29), racially and ethnically diverse men who have sex with men and transgender women affected by HIV across the United States. Using a HIV-status stratified randomized trial design, participants will be assigned into one of three conditions (information-only control, a researcher-driven social network intervention, or a peer-referred social network intervention). Behavioral assessments will occur at baseline, 3, 6, 9 and 12 months; biomarkers (viral load) are scheduled for baseline, 6 and 12 months (for HIV-positive participants). HIV negative/status unknown participants may order through the app up to 3 HIV OraQuick self-tests.

The primary outcome is stratified by HIV status and defined as successful engagement in care (consistent VS for HIV-positive participants and routine testing for HIV-negative participants). The specific aims are: 1) Test whether a smartphone application (app) intervention that promotes usergenerated content and engagement to address intersectional stigma is associated with improvements in the HIV prevention and care continuum (HIV testing, antiretroviral adherence, VS) as compared to an information-only control arm; 2) Explore whether user engagement, as measured by quantitative and qualitative paradata, mediates the intervention's stigma- and HIV care-related outcomes; and, 3) Examine how changes in intersectional stigma and improvements across the HIV care continuum vary between the researcher-driven vs. peer-referred social network intervention conditions. Our research study is innovative given its focus on intersectional stigma as a key target of intervention, and its ability to assess how different kinds of online social network structures influence participants' engagement over time, reduce experiences of intersectional stigma, and improve successful engagement in care. This research addresses a critical need to reduce the effects of multiple stigmas in a priority population using an intervention delivered through a highly appealing, widely utilized technology. If effective, this form of stigma amelioration via online support can be broadly disseminated to reduce HIV transmission and improve care among YBLMT.

STUDY SCHEMA

	Baseline	3 mo	6 mo	9 mo	12 mo
Survey (all pts)	V	✓	✓	✓	✓
HemaSpot (HIV+ pts)	V		✓		✓
HIV Home Test (HIV- pts)	pts may request <=3x and must be >=3 mo apart				

1.0 INTRODUCTION

1.1 Background

Young Black and Latino men who have sex with men (MSM) and transgender women who have sex with men (YBLMT) have the highest rates of new HIV infections compared with non-Hispanic White peers of the same age.¹ Dynamics within YBLMT's social and sexual networks (e.g., stigma, discrimination, social isolation) likely contribute to higher HIV incidence even when engaging in fewer individual-level risk behaviors, ⁵⁴⁻⁵⁶ and limit their continued engagement in the HIV care continuum. ^{12,15,16,19,57-59}

Intersectional stigma impedes efforts across the HIV care continuum by inhibiting protective behaviors (e.g., condom/PrEP use, sustained viral suppression) and decreasing care utilization (e.g., linkage and retention in HIV care). ^{5,6,9,11-18,57,58,60} These effects are particularly severe for YBLMT who face multiple sexual minority-, race/ethnicity-, and HIV-related stigmas, ^{6,10,11,19,61} as these stressors can have additive or multiplicative negative health effects. ^{11,62-68} These overlapping stigmas also foster environments that enable and drive high-risk behaviors ²⁰⁻²² and limit options to build healthy relationships and supportive networks. ^{20,21,23}

Social networks offer powerful means for improving the HIV prevention and care continuum for YBLMT, 31,69-71 yet few interventions have focused on intersectional stigma as a key intervention target for HIV prevention and care. 30,38,41-46 To date, most stigma-focused interventions are delivered in-person, focus on an older or general age range, or exclusively focus on either HIV-positive or HIV-negative populations. The logistical requirements of these interventions may not fit the realities of YBLMT, particularly if they anticipate and/or have experienced stigma. Given that nearly all YBLMT in the United States (U.S.) have regular access to a smartphone, computer, or internet-enabled device, 72,73 the Internet's 4A's: affordability, accessibility, availability, and anonymity may circumvent YBLMT's stigma concerns, facilitate open dialogue, and encourage HIV testing and care through supportive interactions with peers across the country. 48,74-76

Few published eHealth interventions have been developed specifically for YBLMT. 44,48,77-80 While a growing number of studies describe intersectional stigma among YBLMT,81-84 few interventions have addressed intersectional stigma on HIV care outcomes and none have done so for HIVpositive and HIV-negative YBLMT together. HealthMpowerment (HMP), a mobile web-based intervention, was designed to remove logistical, financial, and social stigma barriers⁴⁸ by engaging HIV-positive, negative, and status-unknown YBLMT in a supportive, online community.⁴⁷ HMP provides a platform to capitalize on the strength of social networks. 47,78,85,86 In a randomized controlled trial (RCT) with 474 YBMT (ages 18 – 30; 8.4% also identified as Latinx/Hispanic; 2.7% transgender), the social support features of HMP Original were the most frequently used intervention components. Engagement with these features was associated with improved HIV care outcomes (see Preliminary Findings below). HIV-negative and HIV-positive MSM participants in the original HMP intervention also demonstrated a decrease in condomless anal intercourse (3 months).⁴⁷ Among HIV-positive participants, increases in viral suppression (VS) at 3, 6 and 12 months was seen among both intervention and control participants. 87 In HMP Stigma. we will capitalize on the social support elicited through HMP Original to curtail intersectional stigma and strengthen YBLMT's continued engagement in HIV care (i.e., routine HIV testing for HIV uninfected, and sustained VS for HIV-infected YBLMT).

1.2 Rationale

Across every stage of the HIV care continuum, YBLMT underperform compared to their White peers.²⁻⁴ Among interventions for Black or Latino sexual and gender minorities,²⁶⁻⁴⁶ few focus on intersectional stigma as a key intervention target.^{30,38,41-46} Stigma-reduction interventions are primarily delivered in-person, focus on older ages, or include either HIV-positive or HIV-negative MSM. HealthMpowerment (HMP Original; R01MH093275) was designed to engage HIV-positive, negative, and status-unknown YBLMT and to reduce sexual risk via a mobile optimized online platform.⁴⁷ This approach helped remove logistical, financial, and stigma barriers to intervention participation; however, engagement as measured by detailed data collected as users interact with mHealth interventions (i.e. paradata) varied greatly between participants.⁴⁸ Through a R21 study (MH105292), we explored whether participants in the HMP intervention arm reported reductions in HIV-related stigma outcomes. Using behavioral data and intervention paradata, our mixed-methods results suggest that participants' user-generated content (e.g., discussions in HMP's diverse forums) regarding intersectional stigma was associated with improved psychological well-being and HIV care outcomes.⁴⁹⁻⁵¹

A gap in knowledge exists regarding how participants' engagement with mHealth interventions is linked to HIV prevention and care outcomes. Paradata can provide purposeful process metrics (e.g., timestamps in system logs to quantify time spent using the intervention, types of features used) to assess intervention engagement. We will use paradata to gauge how intersectional stigma and HIV care continuum outcomes differ based on participants' frequency (exposure), time spent (engagement), and types of intervention components participants used (usage) in the app. We will also use paradata to characterize YBLMT's discussions with each other within HMP Stigma social networks, and study how these exchanges influence intervention engagement and HIV care continuum outcomes over time.

We propose to enhance HMP (HMP Stigma) by leveraging the social support elicited through user-generated content to focus centrally on intersectional stigma reduction and promote YBLMT's successful engagement in care. Furthermore, given that paradata can help identify what intervention components should be kept, removed, or redesigned between versions of a smartphone application (app) intervention, 52,53 we will leverage lessons learned from HMP Original alongside feedback from our Youth Advisory Board (YAB) to improve intervention engagement (e.g., expanding HMP's gamification elements, improving chat and upload features). Given that HMP is fundamentally relational in nature, we will also test whether HMP Stigma is as efficacious and engaging when participants are recruited by researchers (i.e., researcher-created HMP network) as compared to being referred by participants themselves (i.e., peer-referred HMP network). This approach offers a unique opportunity to understand who participates in these networks, what network structures emerge, and how peer exchanges differ between the two HMP networks. 99-105 We hypothesize that participants assigned to the peer-referral condition will have greater success in eliciting peer social support, promoting intervention engagement, and achieving the desired stigma- and HIV-related outcomes than participants in the researchercreated HMP network.

We will recruit a sample of 1,050 racially and ethnically diverse men who have sex with men (MSM) and transgender women (ages 15-29) affected by HIV across the United States. Using a HIV-status stratified randomized trial design, participants will be assigned into one of three conditions (information-only control, a researcher-driven social network intervention, or a peer-

referred social network intervention). Behavioral assessments will occur at baseline, 3, 6, 9 and 12 months; biomarkers (viral load) are scheduled for baseline, 6 and 12 months. The primary outcome is also stratified by HIV status and defined as *successful engagement in care* (consistent viral suppression for HIV-positive participants and routine testing for HIV-negative participants). We will also collect mixed-methods paradata (e.g. number of log-ins and posts, total time spent, features used, length and stigma content of posts) to characterize the nature of virtual exchanges between participants and examine if their discussions of intersectional stigma over time result in improvements in HIV outcomes.

Our study is innovative given its focus on intersectional stigma as a key target of intervention. This research addresses a critical and significant need to reduce the effects of multiple stigmas in a priority population using an intervention delivered through a highly appealing, widely-utilized technology. If effective, our intervention can be broadly implemented to address intersectional stigma and to optimize successful engagement in HIV prevention and care among YBLMT.

2.0 STUDY OBJECTIVES

2.1 Primary Objective:

The primary outcome is successful engagement in care, defined as consistent viral suppression for HIV-positive participants and routine testing for HIV-negative participants.

2.2 Secondary Objective:

A secondary objective is whether user engagement, as measured by both quantitative and qualitative paradata, mediates the intervention effects observed in stigma and HIV care outcomes.

An additional secondary outcome is how changes in intersectional stigma and improvements across the HIV care continuum vary between the researcher-driven vs. peer-referred social network intervention conditions.

2.3 Study Hypotheses/Research Questions

Our proposal is built on the scientific premise that network interventions can encourage behavior change. ^{31,90-95} Given that YBLMT widely use social networking sites and applications (apps) to socialize with similar others, ^{28,48,76} HMP Stigma seeks to promote social support by creating a virtual community for YBLMT; thus, we hypothesize that:

A. Compared to YBLMT assigned to an information-only condition, YBLMT assigned to HMP Stigma will report greater reductions in stigma, and be more successful at buffering the negative sequelae of intersectional stigma and circumventing barriers to successful engagement in the HIV care continuum.^{71,96}

3.0 STUDY DESIGN

The study will consist of two phases:

- 1) Refinement and finalization of HMP Stigma
- 2) A three-arm RCT of HMP Stigma

3.1 Study Population

We will enroll 1,050 YBLMT from across the United States into this 3-arm randomized trial. Participants' self-reported HIV status at baseline will be used for allocation in our HIV-status stratified randomization procedure.

3.2 Sample Size

Participants self-reporting as HIV positive at baseline will be randomized across the three arms (N=150 per arm). Participants who self-report being HIV negative or serostatus unknown at baseline will be randomized (N=150 per arm) into either the Information-Only Control (Attention-Control) or the Researcher-Created HMP Network (Intervention Arm 1). Given that we are allowing the 150 HIV-positive participants assigned to the Peer-Referral version of HMP (Intervention Arm 2) to invite two peers into their social network, we do not know the baseline HIV prevalence among recruited peers. To avoid a priori assumptions of who will be invited, we estimate that half will be HIV-negative or sero-unknown.

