Peer-referred HMP Network Arm: Participants randomized to Intervention Arm 2 (peer-referred network) will be enrolled into a parallel (but separate) version of HMP Stigma. The only difference between Arm 1 and Arm 2 is that participants in Arm 2 will have a referral feature in their profile that allows them to earn \$20 in e-gift cards if they successfully refer and enroll 2 peers of their choosing (\$10 per peer) in the first 45 days of their study participation. The referral feature will create a customized link for each participant that can be emailed or text messaged to invite peers into the study. 189 Simple instructions will be provided at enrollment and in the app describing how to refer them. Participants may send referral links until two of their peers have screened eligible and enrolled in the study. Participants may send referrals from Day 1 – 45 of their time in the trial. If two of a participant's referred peers successfully enroll within that time window, at that point, the original participant will receive a notice from the study team that they have successfully reached their referral quota and the referral feature will deactivate. their referral incentives and HMP usernames of their referrals within their profile. While they will be able to see whether their peer has enrolled and what username the peer created, they will not receive any information about any of their peers' survey responses, including those who screened ineligible. Referred peers will see the HMP username of their referrer; they will not be eligible to refer their own peers.

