4.0 SELECTION AND ENROLLMENT OF STUDY PARTICIPANTS

4.1 Inclusion Criteria (All study arms)

- Aged 15-29 years (inclusive) at time of screening
- Identify as Black/African American and/or Latino/Hispanic
- Current U.S. resident (verified by zip code)
- Speak and read English
- Report anal intercourse in the past 6 months
- Assigned male sex at birth (no restrictions on current gender identity)
- Has a smartphone
- If HIV-positive, does not report a hemophilia diagnosis or current use of anti-coagulation medication

Additional Inclusion Criteria (Referred Peers from Peer-Referral Arm)

- Invited by current participant in Intervention Arm 2 (approximately 300 participants)
- Any race/ethnicity

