10.2 Power Estimates

The primary outcome for the proposed trial is stratified by HIV status and defined as *successful* engagement in care. For HIV-positive participants at baseline, we define successful engagement in HIV care as consistent VS across the 12-month trial (per IOM guidelines²¹⁸). For HIV-negative

or sero-unknown at baseline, we define successful engagement in care as participation in routine HIV testing (2 HIV tests with at least 3 months apart from one another, per CDC guidelines²¹⁹). We define power as correctly identifying the difference in the proportions of YBLMT with serospecific engagement in HIV care within 12 months of each intervention arm (2 arms: HMP Stigma with researcher-created network, HMP Stigma with peer-referred network) to the control arm (Information Control), thus powering for 3 independent hypothesis tests. Our sample size calculations are based on pair-wise HIV-stratified comparisons of the 3 groups in terms of proportion of successful engagement using a two-sided significance level of 0.05 altered by the number of comparisons using a Bonferroni adjustment (significance level is 0.017 for 3 comparisons). To have 80% power to detect a minimum effect size (OR=1.9) of successful engagement in care between the 3-arm trial, we will require at least 450 HIV-negative and 450 HIV-positive participants to detect a 17% difference in successful engagement in. In the event of a 20% loss to follow-up, we will have sufficient power to detect an OR=2.1 (18% difference) at alpha=.017. Participants may continue the study even if they miss an assessment intermittently. We will compare those who completed different follow-up interviews with those who did not on key baseline predictors to check for possible sampling bias. Our analysis will use ITT as appropriate.

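### The 450 HIV-negative participants in the power statement assume complete referral fill at a 50% share; any shortfall lowers power for the two HIV-negative contrasts involving Arm 2

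*Combined protocol and SAP*

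**What the plan says.** Section 3.2 randomises participants who report being HIV-negative or of unknown status to control and to Arm 1 only, 150 each. Section 5.1 agrees: 750 people are enrolled directly, 300 of them HIV-negative, and only HIV-positive participants (150) are randomised to Arm 2. The rest of Arm 2 is to be 300 referred peers.

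Section 3.3.2 sets the referral rules. "Participants may send referral links until two of their peers have screened eligible and enrolled in the study", during days 1 to 45, after which the feature is switched off; peers may not refer others. Section 4.1 describes the referred group as "Invited by current participant in Intervention Arm 2 (approximately 300 participants" in all). Section 3.2 fixes the mix of peers: "To avoid a priori assumptions of who will be invited, we estimate that half will be HIV-negative or sero-unknown". Section 5.4.1 lets nominators invite peers of any HIV status.

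Section 10.2 then states that "we will require at least 450 HIV-negative and 450 HIV-positive participants to detect a 17% difference", with 80% power and an odds ratio of 1.9, for pairwise comparisons within HIV stratum, "using a two-sided significance level of 0.05 altered by the number of comparisons using a Bonferroni adjustment" ("significance level is 0.017 for 3 comparisons"). Its only allowance for lost numbers concerns follow-up: "In the event of a 20% loss to follow-up, we will have sufficient power to detect an OR=2.1 (18% difference) at alpha=.017".

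**The concern.** Section 10.2 treats 450 HIV-negative participants as a requirement. A third of them (150) are not under the trial's control: they depend on how many slots the nominators fill and on which peers they choose. The plan enters the largest possible number of peers as if it were the expected number. It gives no yield estimate, shortfall allowance or replacement rule. The 20% in section 10.2 covers people who enrol and are later lost, not peers who never enrol.

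Two of the three HIV-negative contrasts rest on this number: Arm 2 v control, which is part of the primary analysis in 10.3.1, and Arm 2 v Arm 1, which 10.3.1 also tests and which bears on Aim 3. If referral falls short, a null result in either could be read as coming from an adequately powered comparison when it did not.

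**Working it through.** **Inputs from the documents.** Nominators 150; at most 2 enrolled peers each; HIV-negative share 0.5; 150 HIV-negative randomised to control and 150 to Arm 1; two-sided alpha 0.017; difference 17 points; OR 1.9; 80% power.

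**Inputs not in the documents (assumed, shown as ranges).** Referral fill *f*, meaning the fraction of the 300 slots used; a share *h* other than one half; the control success rate.

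**1. The plan's headcount.** Arm 2 HIV-negative n = 300 × *f* × *h*. With *f* = 1 and *h* = 0.5 this is 150, and 150 + 150 + 150 = 450, which matches section 10.2 exactly. In general 450 is reached only when *f* × *h* ≥ 0.5. At *h* = 0.5 that requires *f* = 1.

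**2. The plan's power with full referral (150 v 150).** I used the normal approximation for two proportions:

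- p̄ = (n₁p₁ + n₂p₂)/(n₁ + n₂)
- SE₀ = √[p̄(1 − p̄)(1/n₁ + 1/n₂)]
- SE₁ = √[p₁(1 − p₁)/n₁ + p₂(1 − p₂)/n₂]
- power ≈ Φ[(Δ − z·SE₀)/SE₁], with z = 2.387 for alpha 0.017

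For OR 1.9, power at 0.017 is at most 64.6% (control rate 42%, v 57.9%). The stated 80% is approached only at unadjusted 0.05 (79.0%). OR 1.9 also cannot produce 17 points: its largest difference is (√1.9 − 1)/(√1.9 + 1) = 15.9 points. Taking 17 points alone at 41.5% v 58.5%: SE₀ = 0.0577, SE₁ = 0.0569, and (0.17 − 2.387 × 0.0577)/0.0569 = 0.57, so power is 71%. This shortfall from 80% exists before any referral is missed.

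**3. Effect of under-filling (17 points, 150 controls, alpha 0.017, share 50%).** For example, at 50% fill and 41.5% v 58.5%: n₂ = 75, p̄ = 0.472, SE₀ = 0.0706, SE₁ = 0.0697, and (0.17 − 2.387 × 0.0706)/0.0697 = 0.02, so power is 51%.

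| Fill | Arm 2 HIV-negative n | 41.5% v 58.5% | 20% v 37% | 70% v 87% | Difference detectable with 80% power (centred on 50%) |
|---|---|---|---|---|---|
| 100% | 150 | 71% | 81% | 89% | 18.6 points |
| 75% | 112 | 63% | 75% | 82% | 20.0 points |
| 50% | 75 | 51% | 64% | 68% | 22.6 points |
| 33% | 50 | 38% | 52% | 50% | 26.0 points |

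Arm 1 also has 150 HIV-negative participants, so the same table serves Arm 2 v Arm 1 if the lower rate is read as Arm 1's.

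**4. Effect of the share (power at 41.5% v 58.5%, alpha 0.017; n in brackets).**

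| Fill | Share 30% | Share 50% | Share 70% |
|---|---|---|---|
| 100% | 57% (90) | 71% (150) | 79% (210) |
| 75% | 47% (68) | 63% (112) | 73% (158) |
| 50% | 35% (45) | 51% (75) | 61% (105) |

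These figures treat observations as independent and include no loss to follow-up. Losing 20% of each group at 50% fill and 50% share leaves 120 v 60, with power of 41% at 41.5% v 58.5% and 53% at 20% v 37%.

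**The case against.** Several points can fairly be made for the plan.

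- **150 is not a hard cap.** A reader might infer that the referral scheme cannot yield more than 150 HIV-negative peers. The documents do not support that. Only the total of 300 is capped; the share is a midpoint estimate and section 5.4.1 leaves it unrestricted. A 70% share at 75% fill gives 158. This stands. But a share below half is equally open, and the plan relies on neither.
- **No low yield is shown.** A reader might conclude that the design should be expected to miss 450. The documents give no expected yield, so that is unproven. Links may be sent until two peers have actually enrolled, so an ineligible invitee does not use up a slot; each enrolment is paid; and section 5.4.6 has the DSMB watch for slow accrual and high ineligibility. None of this supplies a power allowance.
- **The power levels depend on the control rate.** A mid-range rate is close to the least favourable placement for a 17-point difference. At 70% v 87%, power still exceeds 80% at 75% fill. The levels move with the rate, but the fall with lower fill appears at every rate examined.
- **Not all of the gap comes from referral.** A reader might set the stated 80% against 51% and blame referrals for the whole. At mid-range rates the step from 80% to 71% belongs to the base calculation at 0.017; only the fall below 71% is due to under-filling.

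**Conclusion.** The point holds within limits. The required 450 HIV-negative participants are reached only if fill times share is at least 0.5; at the plan's own 50% share this means all 150 nominators enrolling two peers in 45 days, with no margin. If fill is lower and the share does not rise to offset it, the single stated power does not hold for HIV-negative Arm 2 v control or Arm 2 v Arm 1. Halving the fill at a 50% share costs about 17 to 21 percentage points of power across the three control rates (81 to 64, 71 to 51, 89 to 68, with rounding). Fill, control rate and any share other than one half are assumptions, so the loss can be given only as a range.

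HIV-negative Arm 1 v control (150 v 150 randomised) and the 450 randomised HIV-positive participants do not depend on referral. It might be inferred that the stated 80% is therefore safe for HIV-negative Arm 1 v control. It is not: at 0.017 that comparison has at most 64.6% for OR 1.9, and about 71% for 17 points at mid-range rates. Full referral at a 50% share would not restore the stated figure for OR 1.9 either.

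**What to change.** - In 3.2 and 10.2, describe 300 as the maximum number of referred peers, and 150 HIV-negative as the number at full fill and a 50% share.
- In 10.2, report power and detectable difference for HIV-negative Arm 2 v control and Arm 2 v Arm 1 over a range of fill (for example 50%, 75% and 100%) and of share (below and above half), at a stated control rate.
- State the HIV-negative Arm 1 v control power separately for 150 v 150, recomputed at 0.017 with an odds ratio and a difference that agree, rather than carrying over 80%.

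The cost is wording, one table and a less favourable stated power for the two Arm 2 contrasts; the recomputed Arm 1 v control figure may also fall below 80%, depending on the control rate. No extra participants and no design change are needed.
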